## 7.5 Investigational Product Accountability and Disposal

Accountability for study drug that is administrated during the course of the study is the responsibility of the Investigator or designee. Investigational clinical supplies must be received by a designated person at the clinical site and kept in a secure and temperature-controlled location. For CC-95251, azacitidine, and venetoclax, the investigational site must maintain accurate records demonstrating dates and amounts of study drug received or obtained from the pharmacy, to whom it was administered (subject-by-subject accounting), and accounts of any vials accidentally or deliberately damaged and/or returned to the Sponsor.

The Sponsor (or designee) will review with the Investigator and relevant site personnel the process for documenting receipt of IP, as well as procedures for accounting, reconciling IP, and documenting this process.

The Sponsor (or designee) will review with the Investigator and relevant site personnel the process for IP return, disposal, and/or destruction including responsibilities for the site versus the Sponsor (or designee).

## 7.6 Investigational Product Compliance

Only the pharmacist or Investigator's designee will dispense CC-95251 and azacitidine. A record of the total dose (and number of vials used) of CC-95251 and azacitidine administered to each subject must be maintained.

Protocol CA059-001 Amendment 3.0

930197534 2.0

Approved v2.0

The pharmacist or Investigator's designee will document the doses dispensed/administered in the appropriate study records and the appropriate eCRF. Study intervention compliance will be periodically monitored by drug accountability, including the review of dosing diary cards. Drug accountability should be reviewed by the study site staff at each visit to confirm treatment compliance. Study sites should discuss discrepancies with the subject at each on-treatment study visit.

- When subjects are dosed at the site, they will receive study intervention directly from the investigator or designee, under medical supervision. The date and time of each dose administered in the clinic will be recorded in the source documents and recorded in the electronic case report form (eCRF). The dose of study intervention and study subject identification will be confirmed at the time of dosing by a member of the study site staff other than the person administering the study intervention.
- When subjects self-administer venetoclax at home, compliance with study intervention will be assessed at each visit. Compliance will be assessed by direct questioning, and counting returned tablets during the site visits, and documented in the source documents and relevant form. Deviation(s) from the prescribed dosage regimen should be recorded in the eCRF.
- Accountability records of study interventions in respective sub-protocols dispensed and administered to each subject must be maintained and reconciled with study intervention and compliance records. Intervention start and stop dates, including dates for intervention delays and/or dose reductions, will also be recorded in the eCRF.

### 8 CONCOMITANT MEDICATIONS AND PROCEDURES

All medications (excluding prior cancer therapy for the tumor under evaluation) taken beginning when the subject signs the ICF and all concomitant therapy during the study

All prior chemotherapy (biologic, immunologic, or radiation therapy) and anticancer surgery prior to the administration of either study drug, will be recorded in the appropriate section of the eCRF.

Packed red cell and platelet transfusion history

The Investigator will instruct subjects to notify the study staff about any new medications taken after signing the ICF. All medications and significant non-drug therapies (herbal medicines, physical therapy, etc.) and any changes in dosing with existing medications will be documented on the eCRFs.

## 8.1 Permitted Concomitant Medications and Procedures

Subject to the precautions described in Section 8.2, the use of any concomitant medication or therapies deemed necessary for the care of the subject should be used. Repeat PK evaluations may be conducted if changes are made to concomitant medications suspected of affecting drug absorption or metabolism.

Prophylactic and/or therapeutic use of medications (eg, antiemetics for nausea and vomiting, antidiarrheals for diarrhea, laxatives and/or stool softeners for constipation) for gastrointestinal disorders are permitted.

Parenteral flu vaccination is permitted.

Routine infectious disease

Subjects may receive authorized or approved COVID-19 vaccines while continuing on study treatment at the discretion of the Investigator. COVID-19 vaccines that are NOT live are allowed and should be handled in the same manner as other vaccines. Administration may occur during the study, including during the administration of the BMS study treatment and after the last administration of the BMS study treatment.

Treatment of active SARS-CoV-2 infections or high risk exposures, including use of investigational therapies, is allowed and should be discussed with the Sponsor's medical monitor.

### 8.2 Prohibited Concomitant Medications and Procedures

Other investigational therapies must not be used while the subject is on the study.

Anticancer therapy (chemotherapy, biologic or investigational therapy, and surgery) other than the study treatments must not be given to subjects while the subject is on the study. If such treatment is required, the subject must be discontinued from the study.

[figure not shown]

Table 12: Management of Potential Venetoclax Interactions with CYP3A and P-gp Inhibitors

Cycle Day	Moderate CYP3A or P-gp Inhibitor a	Strong CYP3A Inhibitors (Other than Posaconazole) b	Posaconazole c
Day 1	50 mg	10 mg	10 mg
Day 2	100 mg	20 mg	20 mg
Day 3	200 mg	50 mg	50 mg
Day 4 and beyond	200 mg	100 mg	70 mg

Abbreviations: CYP = cytochrome P450; P-gp = P-glycoprotein.

 Based on in vitro data, azacitidine metabolism does not appear to be mediated by CYPs; therefore, CYP inhibitors and inducers are unlikely to have any impact on the metabolism of azacitidine. Clinically relevant inhibitory or inductive effects of azacitidine on the metabolism of CYP substrates are unlikely.

<sup>a Following discontinuation of the CYP3A or P-gp inhibitor: 2 to 3 days after the inhibitor is discontinued, resume the venetoclax dose that was used prior to initiating the CYP3A or P-gp inhibitor.

b For subjects who have completed dose escalation and are on a steady daily venetoclax dose, reduce the venetoclax dose to 100 mg once daily when a strong CYP3A inhibitor (other than posaconazole) must be used concurrently.

<sup>c For subjects who have completed dose escalation and are on a steady daily venetoclax dose, reduce the venetoclax dose to 70 mg once daily when posaconazole must be used concurrently.

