All treatments will be administered in 28-day cycles. To optimally benefit from the treatment, Investigators should aim to treat subjects for at least cycles, although subjects can be discontinued from the protocol earlier if they demonstrate documented relapse from CR or partial remission (PR), disease progression, unacceptable adverse event(s), intercurrent illness that prevents further administration of treatment, investigator's decision to withdraw the subject, subject withdraws consent, pregnancy of the subject, noncompliance with trial treatment or procedure requirements, or administrative reasons. Subjects may continue treatment if they are deriving benefit from treatment without unacceptable toxicity (any CR, MLFS, PR, or stable disease [SD] with demonstrated clinical benefit eg, reduction in transfusion burden), as judged by the Investigator, or until disease progression, loss of clinical benefit, unacceptable toxicity, or decision to withdraw by subject or Investigator. Subjects who discontinued one study treatment in a combination arm for reasons other than relapse or resistant disease may continue on the non-discontinued drug(s) if the subjects are receiving benefit as per Investigator's discretion until there is evidence of relapse or resistant disease, or until they are no longer able to tolerate treatment due to an adverse event (AE). Retreatment (within from last dose of CC-95251 in the prior study treatment period) will be permitted (refer to Section 7.2.7.9 for details). Subjects may be retreated only once during the study and the total duration in the study will be no longer than 4 years from the original C1D1.

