## Follow-up Period

All subjects will be followed for days after the last dose of study drug for AE reporting. In addition, serious adverse events (SAEs) made known to the Investigator at any time thereafter that are suspected of being related to study drug are to be reported until such SAEs have recovered (returned to baseline), recovered with sequelae, or death (due to the SAE). Subjects will also be followed for all AEs (SAEs and non-serious AEs) associated with confirmed or suspected severe acute respiratory syndrome coronavirus 2 (SARS-CoV-2) infection until resolution, the condition stabilizes, the event is otherwise explained, the event is deemed irreversible, the subject is lost to follow-up, or for suspected cases, until SARS-CoV-2 infection is ruled-out (Section 6.3.1).

Subjects who discontinue treatment for reasons other than disease progression (or relapse) or start of a new anticancer therapy will have efficacy evaluations (refer to Section 6.3.2) up to a maximum of or until progression of disease (or relapse), initiation of a new anticancer therapy, withdrawal from the study, death, or the End of Trial, whichever comes first.

All subjects will be followed starting from the end of treatment according to the schedule for the efficacy long term follow-up (refer to Section 6.3.2), for survival for up to or until death, lost to follow-up, or the End of Trial, whichever occurs first. Survival follow-up may be conducted by record review (including public records) and/or telephone contact with the subject, family, or the subject's treating physician.

During follow-up, information (including dates) on new anticancer therapies will be collected until withdrawal from the study, death, or the End of Trial, whichever comes first.

The study will be conducted in compliance with International Conference on Harmonisation (ICH) Good Clinical Practices (GCPs).

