### 1.4.2 Risk Assessment

The proposed study design includes various components aimed at limiting potential risks to study subjects. The subject population will not include individuals, such as children or mentally disabled adults, who are not capable of expressing themselves in the same way as mentally competent adults, in order to detect any potential harm to the subjects as early as possible. Standard eligibility criteria are included to ensure acceptable baseline organ function (including hematopoietic function) and lack of clinically significant comorbid diseases. Specific precautions for early development include use of a study design with dose escalation and subsequent expansion, a defined DLT observation period and DLT monitoring, staggered enrollment, hospitalization for observations as specified in the study protocol, as well as SRC oversight built into the protocol. Subjects will be monitored for possible toxicity throughout the study by physical examination, vital sign and AE collection, through standard and specialized laboratory tests including complete blood counts, serum chemistries, and electrocardiogram (ECG), and observed for survival follow-up starting from the last dose of the investigational agent for up to or until death, lost to follow-up, or the end of study, whichever occurs first. Study subject monitoring and guidelines for

management for select AEs of interest for the study drug are included in the study protocol (Section 7.2.7.8).

The will be utilized to guide CC-95251 dose escalation/de-escalation decisions, with the final recommendation being made by the SRC. Additionally, the protocol defines the criteria in the dose escalation (Part A) that must be met prior to opening enrollment to cohorts testing CC-95251 in combinations with azacitidine or with venetoclax and azacitidine in the relapsed/refractory setting. The protocol also specifies that testing of combinations in newly diagnosed MDS or AML populations in dose expansion may only occur

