## **Table 2:** Study Objectives

## **Exploratory Objective(s)**

The exploratory objectives are:

- To explore the relationship between dose and systemic exposure of CC-95251 and measures of toxicity, efficacy, and PD biomarkers.
- To evaluate molecular and/or cellular biomarkers in the bone marrow and blood that may be associated with efficacy of CC-95251
- To evaluate the minimal residual disease (MRD) status, by flow cytometry and/or relevant gene sequencing methods

Abbreviations: ADA = anti-drug antibodies; AML = acute myeloid leukemia; MDS = myelodysplastic syndromes; MRD = minimal residual disease; PD = Pharmacodynamics; PK = pharmacokinetics.

**Table 3:** Study Endpoints

Endpoint	Name	Description	Timeframe
Primary	Safety	DLTs evaluated using the NCI CTCAE criteria, Version 5.0. Adverse events, including TEAEs, laboratory assessments, ECG results, ECOG performance status, and vital signs	Dose escalation and dose expansion  Screening to after the last dose of study treatment
Secondary	Preliminary efficacy a	Complete remission rate (CRR) (as assessed by the Investigator) for AML according to the modified European Leukemia Net (ELN) response criteria (CR + CRh + CRi), ORR (CR + CR MRD . + CRh + CRi + MLFS + PR)  CRR (as assessed by the Investigator) for MDS according to the modified IWG Response Criteria	Dose expansion Day 1 to end of follow up
		(CR), ORR (CR + CRh + marrow CR + PR)  Duration of remission, duration of response, stable disease rate (MDS only), relapse-free survival, event-free survival, progression-free survival, time to remission/response, transfusion independence, time to AML transformation for MDS subjects, OS rates at 6 and 12 months	
Secondary	Pharmacokinetics (PK)	Estimate parameters including but not limited to C max , C min , C trough , AUC (0-T) , AUC (TAU) , t max , CLT, and accumulation index of CC-95251, when feasible as a single agent and in combination with antineoplastic agents in AML and MDS	Dose escalation and dose expansion  Day 1 to 8 weeks post-dose of CC-95251
Secondary	Anti-drug Antibody (ADA)	Determine the presence and frequency of anti CC-95251 antibodies (ADAs) using a validated electrochemiluminescence (ECL) assay	Dose escalation and dose expansion  Day 1 to 8 weeks post-dose of CC-95251

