## 3.1.5.3 Follow-up Period

All subjects will be followed for after the last dose of study drug for AE reporting. In addition, serious AEs (SAEs) made known to the Investigator at any time thereafter that are suspected of being related to study drug are to be reported until such SAEs have recovered (returned to baseline), recovered with sequelae, or death (due to the SAE). Subjects will also be followed for all AEs (SAEs and non-serious AEs) associated with confirmed or suspected SARS-CoV-2 infection until resolution, the condition stabilizes, the event is otherwise explained, the event is deemed irreversible, the subject is lost to follow-up, or for suspected cases, until SARS-CoV-2 infection is ruled-out (Section 6.3.1).

Subjects who discontinue treatment for reasons other than disease progression (or relapse) or start of a new anticancer therapy will have efficacy evaluations of CBC and PBS performed every

All subjects will be followed starting from the end of treatment according to the schedule for the efficacy long term follow-up (refer to Section 6.3.2) for survival for or until death, lost to follow-up, or the End of Trial, whichever occurs first. Survival follow-up may be conducted by record review (including public records) and/or telephone contact with the subject, family, or the subject's treating physician.

During follow-up, information (including dates) on new anticancer therapies will be collected until withdrawal from the study, death, or the End of Trial, whichever comes first.

The study will be conducted in compliance with the International Council on Harmonisation (ICH) of Technical Requirements for Registration of Pharmaceuticals for Human Use/Good Clinical Practice (GCP) and applicable regulatory requirements.

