## 3.2 Study Duration for Subjects

Enrollment is expected to take approximately 24 to 36 months to complete (approximately 16 to 19 months for dose escalation and approximately 12 to 18 months for dose expansion). The entire study is expected to last up to approximately 3 to 4 years.

An individual subject will be in the study for including treatment and follow up unless, the SRC decides to extend the treatment period.

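### Section 8.2 removes from the study a subject who needs other anticancer therapy, while the follow-up sections keep that subject in survival follow-up; the wording must be reconciled

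*Combined protocol and SAP*

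**What the plan says.** Section 8.2 (Prohibited Concomitant Medications and Procedures) says that anticancer therapy other than the study treatments "must not be given to subjects while the subject is on the study". The next sentence is the one at issue: "If such treatment is required, the subject must be discontinued from the study". No readable text in 8.2 narrows either sentence to study treatment or to the Treatment Period.

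The follow-up provisions run the other way. Section 3.1.5.3 states: "All subjects will be followed starting from the end of treatment according to the schedule for the efficacy long term follow-up". That follow-up is for survival, and it ends at a time limit (blacked out), death, loss to follow-up or End of Trial. The Protocol Summary and Section 6.3.3 give the same stopping events. Section 1.4.2 has subjects "observed for survival follow-up starting from the last dose of the investigational agent for up to or until death, lost to follow-up", or end of study (its time limit is also blacked out). New anticancer therapy is in none of these lists. The Protocol Summary and Sections 3.1.5.3, 6.3.2 and 6.3.3 also provide for recording new anticancer therapies during follow-up.

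Section 6.4 covers the case directly. Subjects who stopped study treatment because of relapse, progression or the start of a new anticancer therapy stay in follow-up, by site visit or telephone.

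The endpoint that depends on this follow-up is in Table 3, among the secondary efficacy endpoints: "time to AML transformation for MDS subjects, OS rates at 6 and 12 months". Section 9.6 plans Kaplan-Meier analyses for time-to-event endpoints and reports the survival rate at those two times.

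**The concern.** The sentence in 8.2 is mandatory, and it concerns the study, not the drug. A site that follows it takes the subject out of the study. A site that follows 3.1.5.3, 6.3.3 and 6.4 keeps the subject in. In a multicenter trial, sites could then handle the same event differently.

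Overall survival is at stake because of why the event occurs. In these diseases, other anticancer therapy is typically needed when the leukemia or MDS has relapsed, progressed or not responded. Kaplan-Meier estimation assumes that subjects censored at a given time have the same later risk of death as those still followed. Ending follow-up when new therapy is needed would tie censoring to prognosis, and that assumption would be in doubt.

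**Working it through.** The protocol states no figure on this point and none can be derived from it, so the check is a comparison of texts.

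1. **What ends survival follow-up.** The Protocol Summary and Sections 3.1.5.3 and 6.3.3 name the population as all subjects. They list death, loss to follow-up and End of Trial beside the blacked-out time limit. The redaction hides only a duration; the population and the other stopping events can be read.

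2. **What new therapy does end.** In the Protocol Summary and Section 6.3.2, starting a new anticancer therapy ends the efficacy evaluations. It is listed for that purpose and not for survival follow-up, so the protocol distinguishes the two.

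3. **How the subject is classed.** Section 6.4 describes these subjects as having discontinued study treatment and continues to follow them. The Protocol Summary does likewise when it refers to "Subjects who discontinue treatment for reasons other than disease progression (or relapse) or start of a new anticancer therapy", which makes new therapy a reason for stopping treatment.

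4. **Whether study can simply be read as treatment.** Section 11 keeps them apart: 11.1 lists reasons for stopping investigational product and 11.2 lists reasons for leaving the study. The 11.2 list is screen failure, withdrawal by subject, completion, death, loss to follow-up and an open category for other reasons. New therapy is not named. It is not named in 11.1 either, which also has an open category. Section 3.2 says "An individual subject will be in the study for including treatment and follow up" (a duration is blacked out inside that phrase), so time in the study includes follow-up.

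5. **The preceding sentence of 8.2.** If being on the study includes follow-up, the prohibition would cover the very therapies that follow-up is set up to record. Read literally, 8.2 would also require removal from the study because of those therapies. The literal reading therefore leaves the recording provisions with little purpose.

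6. **What must happen before survival data are affected.** Three conditions are needed together:
   - a site applies 8.2 literally, against the follow-up sections;
   - vital status is not recovered afterwards, although the Protocol Summary and 3.1.5.3 allow review of records, including public records;
   - the analysis censors the subject at the date of discontinuation.

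7. **Direction.** If those removed would have died sooner than those still followed, the Kaplan-Meier rate is too high. If effective later therapy lets them outlive subjects who progress and stay under follow-up, it can be too low. The documents give no post-progression survival, no share of subjects receiving later therapy and no readable cohort sizes, so neither sign nor size can be fixed.

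Steps 1 to 4 establish the contradiction. Steps 3 and 5 point to the likely intent, which is discontinuation of study treatment only.

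**The case against.** The best defence is that the documents largely resolve the conflict themselves. Section 8.2 belongs to the chapter on concomitant medications, whose natural subject is therapy given alongside study drug. The sections that govern follow-up are specific, agree with each other and, in 6.4, address this exact situation. Loose wording occurs elsewhere too: the Protocol Summary says "subjects can be discontinued from the protocol earlier if they demonstrate documented relapse from CR or partial remission (PR), disease progression" where stopping treatment seems to be meant, and Section 10.3 speaks of an abnormal laboratory value leading to discontinuation from the study. Most sites would probably follow the specific sections.

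Much of this stands, and it keeps the point minor. It does not remove it. The Protocol Summary sentence is permissive and the one in 10.3 is a criterion for calling a laboratory value an adverse event. The sentence in 8.2 is an instruction that a site must carry out. The open category in 11.2 would let a site record the literal reading without any apparent deviation.

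A reader might also infer that the protocol has no rule on censoring overall survival at new therapy. That is not supported. Table 3 attaches a footnote to the preliminary efficacy endpoints, and its text cannot be read in this copy.

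**Conclusion.** The contradiction is real, in current operative text, and minor. Confidence is high for the wording and does not extend to any consequence.

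The effect is zero if sites follow the follow-up sections. Otherwise it depends on all three conditions in the working, and the documents determine neither its direction nor its size. The endpoint exposed is overall survival at 6 and 12 months, a secondary endpoint in a Phase 1 study whose analyses are all described as descriptive. No readable decision rule rests on it. Safety, the recommended Phase 2 dose, complete remission rate and objective response rate are not shown to be affected.

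A reader might infer that the survival estimates will be biased, or that the trial forbids later therapy during follow-up. The documents support neither: the first needs conditions that nothing shows will occur, and the second is at odds with the planned recording of such therapy.

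**What to change.** Reconcile Section 8.2 with Sections 3.1.5.3, 6.3.2, 6.3.3, 6.4 and 11.2. The revised sentence should say that starting non-protocol anticancer therapy does not by itself end study participation or survival follow-up. The prohibition just before it should be read through at the same time, so that its reference to being on the study does not conflict with recording new therapies in follow-up. When study treatment is stopped stays as it is; this point takes no position on that.

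The cost is about one sentence in 8.2, which could go into the next amendment. No new data collection is needed, because follow-up by visit, telephone and record review is already planned.
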